17. DATA ANALYSIS PLAN

This is a pilot study for mechanistic understanding of the relationship between our previously discovered NPS-shared neural circuit and study partner-rated NPS. Results from the study will provide information for accurately calculating effect size for future clinical trial. Regardless, in addition to follow the rule of 12-20 subjects per group for a pilot clinical trial, we will calculate the sample size. The sample size calculation is based on the effect size of LPG related tDCS on visual attention performance ($f = 0.45$, $n = 36$). Additionally, the effect size of correlation between NPS-shared neural circuit and patient-report NPI-Q was $r^2 = 0.70$ in our previous study³ – here we use a much more conservative estimation at $r^2 = 0.20$, the sample size will be $n = 37$. All of these calculations are based on power at 0.80 and alpha at 0.05. For an 8-week follow up, we estimate 10% attrition rate. Therefore, we propose a total of 40 intervention subjects for the study.

Aim 1. Determine the effect of tDCS on NPS-shared neural circuit. H: After intervention, the active, relative to sham group will have greater increase in LPG activity, indexed by greater activation in LPG in response to visual attention task (H1a) and greater increase in resting FC strength between LPG and other regions within the NPS-shared neural circuit (H1b). To assess the activation pattern in LPG, we will conduct GLM analysis with the SPM software. The coefficients of GLM corresponding to LPG will be analyzed through hypothesis testing. We will first conduct a simple t-test to evaluate whether the intervention increases LPG activation for each group (at 4 or 8 weeks), and then a more powerful two sample kernel test will be used to test activations distribution difference between groups.⁵¹ Similarly, we will take the FCs between LPG and other regions as a multivariate covariate and apply the two-sample kernel test to evaluate group difference in the change of LPG FC pattern after intervention (at 4 or 8 weeks). In addition, simple multiple testing for each connection will be used as a screening procedure to identify a subset of connections included in the kernel test.

Aim 2. Determine the relationship between NPS-shared neural circuit and study partner-report NPS.

H2a. After intervention, the active, relative to sham group will have greater improvement in study partner-rated NPS in terms of lower severity and fewer co-existing symptoms: We will fit linear mixed-effect models for changes in NPS: $Y_i = X_i\beta + Z_iu_i + \epsilon_i$, where $Y_i = (y_{i1}, \dots, y_{iT})$ represents the NPI measures across time, X_i is a $T \times p$ design matrix for the fixed effects and Z_i is a $T \times q$ matrix for the random effects. The models will include fixed effects such as data collection visit (categorical variable), group, visit and group interaction, and covariates identified as being imbalanced among groups. Stepwise variable selection based on Akaike Information Criteria will be used to select the fixed effects for inclusion. A random participant-specific effect will be included to account for correlation between visits for the same participant. The model-based average within-group change will be computed for each outcome at 4 and 8 weeks. This will allow us to rank the groups in terms of average within-person gains in each outcome. We will conduct a composite hypothesis test to assess if the changes at 4 or 8 weeks differ by groups (similar to a one-factor ANOVA but accounting for repeated measures). **H2b. FC change in NPS-shared neural circuit will contribute to the improvement in study partner-rated NPS across groups:** We will perform epsilon-intensive support vector regression (SVR) with RBF kernel using LIBSVM library.⁵² The Leave-One-Out-Cross-Validation scheme will be applied: each intervention subject will be designated as

the test sample once, while the remaining intervention subjects will be used as training sample. All training sample's features (change of voxel activation from the task or change of FCs from the NPS-shared neural circuit after intervention) will be trained to predict the test sample's outcome (change of NPI severity or frequency score). We will then perform model fitting of the raw and predicted NPI using linear function ($f(x)=ax+b$). Adjusted R^2 will be used to estimate goodness of fit for the model.

Exploratory aim. Examine the relationship between (a) NPS and (b) the coherence between structural and functional aspects of the NPS-shared neural circuit. We will conduct a connectome-based analysis to find structural connections that are unique to severity of NPI. The TN-PCA method⁵³ will be used to correlate with severity of NPI. We can replace the high dimensional tensor network summarizing an individual's brain connectome with a K-dimensional vector of brain PC scores; these scores can be used for visualizing variation among individuals in their brain connectomes and in statistical analyses studying relationships between structural and functional aspects of NPS-shared circuit and covariates. We will compare similarities of involved brain regions of NPS circuit for FC and WM across the entire sample at baseline. Quantitatively, we will use the Dice similarity coefficient to evaluate the percentage of overlapped regions. **To examine whether tDCS' effects on NPS-shared neural circuit and study partner-rated NPS depend on baseline WM integrity,** first we will compare the correlations between FC (at different time points) and baseline WM integrity on the overlapped regions between active vs. sham tDCS groups. We expect to see a higher correlation between FC and WM in active group in later time points. Next, using SVR described earlier⁵² we will examine the relationship between the sample's features (baseline WM tracts) and outcome (change of NPI severity or frequency scores).

Blood analysis plan: We will compare AD pathology markers from blood with changes of NPS, cognitive measures, and MRI data using correlational analyses. We will also examine if individuals with positive AD pathology respond differently to tDCS compared to those with negative AD pathology using ANOVA.

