Exploratory aim. Examine the relationship between NPS and the coherence between structural and functional aspects of the NPS-shared neural circuit. Cumulative literature suggests that white matter (WM) tracts play a critical role in supporting and shaping brain function.¹³ It is often assumed that FC is dependent on underlying anatomical connections,¹³⁻¹⁵ with decreases in WM integrity in dementia related to reduced functional efficiency.¹⁶ The magnitude of correlation between the structural and functional aspects of NPS-shared neural circuit may implicate the severity of NPS. Here, we will collect diffusion tensor imaging (DTI) at baseline, as part of MRI data acquisition, and examine whether the effects of tDCS on NPS-shared neural circuit and study partner-rated NPS depend on WM integrity. Exploring this question will provide broaden our mechanistic understanding of NPS.

We propose that probing the LPG via tDCS provides a way to experimentally test the causal relationship between our previously discovered NPS-shared neural circuit and study partner-rated NPS. The proposed research is highly innovative, while scientifically grounded, for targeting one brain region that may affect multiple NPS. Validating the hypotheses has the potential to support a future R01 study that directly conducts a Stage 2 trial addressing NPS in MCI or AD, thus ultimately improving patients' quality of life and reducing the caregiver burden.

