4. STUDY DESIGN

This is a Stage 0 study for mechanistic understanding. We will recruit older adults with study partner-rated NPS that has worsened in the past 2 years. Our previous study shows that this will capture

the most detrimental type of NPS.¹ We will focus on the MCI group, since understanding and modifying NPS among this group may assist in slowing the progression of dementia. See Table 1 for the overview of assessment and intervention timeline.

- Double-blind randomized controlled trial of 40 participants and their study partner subjects; all eligible and interested intervention subjects will be enrolled and undergo a baseline assessment, MRI scan, and blood draw; PI, staff conducting follow-up assessments and intervention subjects and their study partner subjects will be blinded. Interventionists and data managers will know randomization.
- After baseline, all intervention subjects will be randomly assigned to one of two groups - active anodal or sham C3 tDCS. A MATLAB block-based randomization code will be used to randomly assign study ID to group. Each study ID-group pairing will be printed and placed inside a sealed envelope labeled with only the study ID to ensure blinding. After an intervention subject and their partner subject finish baseline assessments, the interventionist or data manager will open the randomization envelope to assign the respective study ID.
- All intervention subjects will undergo a total of fourteen (14) 20-minute tDCS sessions over the course of four weeks: ideally, five times a week for two weeks, followed by twice a week for an additional two weeks. However, we will extend the intervention for additional two weeks for make-up sessions.
- Assessments will occur at baseline, within 2-week after finishing intervention (post-intervention assessment), and 4 to 6 weeks after post-intervention assessment (follow-up assessment).
- Unblinding will occur upon the completion of the follow-up assessment. We will not provide those in the sham group with the active tDCS procedure.

Primary endpoints:

- Resting-state and visual attention task-related fMRI;⁴⁵

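### Section 17 says the results will allow an accurate effect size for a later trial, but about 18 per arm gives a 95% interval of roughly ±0.65 to 0.69 SD, and no between-arm estimate with an interval is planned

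*Combined protocol and SAP*

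**What the plan says.** The opening of section 17 (Data Analysis Plan) describes a mechanistic pilot and says that its results will provide information for "accurately calculating effect size for future clinical trial". Section 1 adds, on what may follow: "Validating the hypotheses has the potential to support a future R01 study", which would run a Stage 2 trial.

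The size is set in the same paragraph of section 17. It gives n = 36 from f = 0.45 and n = 37 from a squared correlation of 0.20. It then says "All of these calculations are based on power at 0.80 and alpha at 0.05", "For an 8-week follow up, we estimate 10% attrition rate" and "Therefore, we propose a total of 40 intervention subjects for the study". Section 4 gives two groups: "all intervention subjects will be randomly assigned to one of two groups - active anodal or sham C3 tDCS". Randomisation is by blocks, but no allocation ratio is given.

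The planned outputs in section 17 are:

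- **LPG activation (H1a):** a t-test within each group, then a two-sample kernel test between groups.
- **LPG connectivity (H1b):** the same kernel test on the multivariate pattern, after connection-by-connection screening.
- **NPI (H2a):** a mixed model with fixed effects chosen stepwise by AIC, within-group average changes at 4 and 8 weeks, a ranking of the groups, and a composite test of whether the changes differ.
- **Brain-to-NPI prediction (H2b):** support vector regression summarised by adjusted R².

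No precision target is stated for any of these.

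**The concern.** Estimating an effect for later use is a stated purpose of this trial, so it can be tested against the design. Two things look wrong. First, 18 to 20 subjects per arm estimate a standardised difference only roughly, and nothing in the section qualifies the word accurate. Second, the analyses listed lean on tests and within-group changes. A kernel test says whether two distributions differ; it does not give a difference in mean activation. Within-group changes and a ranking do not give a between-arm difference with its uncertainty.

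At stake is what a reader may take from the trial. H1a and H2a are directional claims about active against sham. Without an interval, a reader cannot see that one result may be compatible with both a negligible and a very large effect.

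**Working it through.** **Inputs from the documents.** Total 40; attrition 10%; two groups; power 0.80; alpha 0.05; f = 0.45, which is d = 2f = 0.9 for two equal groups; r² = 0.20.

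**Assumptions.** 1:1 allocation and two-sided alpha; neither is stated.

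**The plan's own figures.**

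- Attrition: 36 / (1 − 0.10) = 40, as stated.
- Correlation: ((1.960 + 0.842) / atanh(√0.20))² + 3 = 36.9, so 37, as stated.
- The n = 36 for f = 0.45 does not reproduce with a plain two-group, two-sided test, which needs 41 (power 0.746 at 36). That is a separate matter, and the point here does not depend on it.

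**Completers per arm.** 40 × 0.90 = 36, or 18 per arm; 20 per arm with no attrition.

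**Precision.** With n per arm, SE(d) = √(2/n + d²/(4n)) and the 95% half-width is 1.96 × SE.

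| n per arm | d | SE | Half-width | 95% CI |
|---|---|---|---|---|
| 18 | 0 | 0.333 | 0.65 | −0.65 to 0.65 |
| 18 | 0.9 | 0.350 | 0.69 | 0.21 to 1.59 |
| 20 | 0 | 0.316 | 0.62 | −0.62 to 0.62 |
| 20 | 0.9 | 0.332 | 0.65 | 0.25 to 1.55 |

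For n = 18 and d = 0.9: √(2/18 + 0.81/72) = √(0.1111 + 0.0113) = 0.350, and 1.96 × 0.350 = 0.69. Noncentral-t intervals agree: 0.21 to 1.58 at 18 per arm and 0.24 to 1.55 at 20.

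**What that width means.** A two-arm trial with 80% power needs 2(1.960 + 0.842)²/d² per arm. Over the limits 0.214 and 1.586 this runs from 342 down to 7 per arm. This only illustrates the spread; the plan does not prescribe this use.

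**Baseline adjustment.** In raw-SD units, with baseline correlation ρ, the half-width near zero effect is 1.96 × √((2/n)(1 − ρ²)). At 18 per arm it is 0.57 for ρ = 0.5 and 0.47 for ρ = 0.7. Both correlations are assumed; the documents give none.

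**Hypothetical selection.** Suppose the next trial were sized on the observed d, and only after a significant pilot. At 18 per arm, significance needs an observed d above 2.03 × √(2/18) = 0.68. Simulated pilots gave:

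| True d | Mean d among significant pilots | Inflation | Real power at the median planned size |
|---|---|---|---|
| 0.9 (plan's f) | 1.07 | 1.2-fold | about 66–69% |
| 0.5 (assumed) | 0.91 | 1.8-fold | about 37% |

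Without selection on significance, the mean observed d is nearly unbiased: 0.51 and 0.92 for true values of 0.5 and 0.9.

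**The case against.** The sentence is rationale. The plan says only that results will provide information towards an effect size, and it then justifies 40 subjects separately by power. Correcting it changes no endpoint, test or sample size. Pilots are small by nature, and the mixed model for the NPI may narrow the interval through repeated measures. The kernel test and support vector regression do not produce a standardised difference, so the figures above do not describe those analyses.

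Much of this stands. The point asks for no more subjects, and the interval applies to scalar endpoints only. But the word accurate is unqualified, and an adjusted half-width of 0.47 to 0.57 SD does not earn it. The mixed model could yield a between-arm difference through its visit-by-group term. Section 17, however, asks only for within-group changes, a ranking and a composite test.

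A reader might go further and infer that the sponsor will size the next trial on the observed effect, so that it will be badly underpowered. The documents do not support that. Section 17 gives no sizing rule, and section 1 says only that validated hypotheses could support a later study. Neither mentions the point estimate or proceeding only after significance. The 1.8-fold inflation also needs a true d of 0.5, which appears nowhere in the documents; at the plan's own d = 0.9 it is about 1.2-fold.

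**Conclusion.** The point holds as one of wording and reporting. With 36 completers split equally, the between-arm standardised difference is known to about ±0.65 SD near zero and ±0.69 SD at d = 0.9. That is not accurate by any ordinary use of the word, and plausible baseline adjustment does not change the conclusion. Unequal arms would widen the interval.

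Separately, the plan commits to no between-arm estimate with a confidence interval for the endpoints behind H1a, H1b and H2a, so even the imprecise estimate is not a specified output.

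The planned tests are not invalidated. The selection figures show what one possible use of the result would do; they are not a property of this trial.

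**What to change.** In section 17, replace the sentence about the future trial with: *The study will give a preliminary estimate of the between-arm effect with its 95% CI, and of the SD, visit correlation and attrition.*

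Alongside the kernel tests, commit to reporting the between-arm difference in change, with 95% CI, for the scalar endpoints:

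- mean LPG activation;
- each LPG connection, or a mean connectivity summary;
- NPI severity and symptom count.

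How a later trial is sized need not be fixed in this plan.

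The cost is a slightly less favourable stated aim and a few more intervals in the report. Sample size and conduct do not change.

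### Forty enrolled less 10% attrition leaves 36, one short of the plan's own n = 37, and the n = 36 given for f = 0.45 cannot be reproduced from the inputs stated

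*Combined protocol and SAP*

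**What the plan says.** Section 17 justifies the sample size in two ways. The first is a rule of thumb: "in addition to follow the rule of 12-20 subjects per group for a pilot clinical trial, we will calculate the sample size".

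The second is a pair of power calculations. One concerns the effect of stimulation on task performance: "The sample size calculation is based on the effect size of LPG related tDCS on visual attention performance", given as f = 0.45 with n = 36. The other concerns the correlation between the neural circuit and the symptom score: "here we use a much more conservative estimation at $r^2 = 0.20$, the sample size will be $n = 37". Both share one sentence of inputs: "All of these calculations are based on power at 0.80 and alpha at 0.05". Attrition and the total follow: "For an 8-week follow up, we estimate 10% attrition rate. Therefore, we propose a total of 40 intervention subjects for the study".

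For f = 0.45 the paragraph names no test, sidedness, number of measures, correlation between measures or covariate. The planned analyses appear later in the same section and are not linked to f. Aim 1 uses within-group t-tests and a two-sample kernel test between groups. Hypothesis H2a uses a mixed model with a composite test of change, described as "similar to a one-factor ANOVA but accounting for repeated measures". Section 4 sets three assessments, starting: "Assessments will occur at baseline, within 2-week after finishing intervention (post-intervention assessment", with a later follow-up.

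**The concern.** When a plan states two required sizes and an attrition rate, the enrolled number should deliver the larger size after losses. Here 36/0.9 is exactly 40, so the total appears to have been built on the smaller size.

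The f = 0.45 calculation raises a different problem. The trial has two groups, and the obvious two-group reading of f = 0.45 does not give 36. A reader cannot tell which test was powered, or whether it resembles the between-group comparisons that will be run. The plan offers the 80% figure in addition to the pilot rule and says that its results will feed effect sizes for a later trial, so the figure should be checkable.

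**Working it through.** **Inputs.** From section 17: f = 0.45 with n = 36; r² = 0.20 with n = 37; power 0.80; alpha 0.05; attrition 10%; total 40. From section 4: two groups. Assumed because not stated: equal allocation, and two-sided tests unless noted.

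**1. Reproducing n = 37.** With r = √0.20 = 0.447 and atanh(r) = 0.4812, Fisher's z gives

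n = ((1.960 + 0.842)/0.4812)² + 3 = 36.9, rounded up to 37.

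The plan's figure reproduces.

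**2. Attrition.** 40 × 0.9 = 36, below 37. In the other direction, 37/0.9 = 41.1, so 42 enrolled. Even the looser 37 × 1.1 = 40.7 rounds up to 41. By contrast, 36/0.9 = 40 exactly.

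**3. Cost in power for r² = 0.20.** Power = Φ(0.4812 × √(n − 3) − 1.960).
- n = 37: Φ(2.806 − 1.960) = 0.801.
- n = 36: Φ(2.764 − 1.960) = 0.789.

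The loss is about one percentage point.

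**4. Trying to reproduce n = 36 for f = 0.45.** For two equal groups d = 2f = 0.90. The noncentral t has noncentrality d × √(n₁n₂/(n₁ + n₂)) and n₁ + n₂ − 2 degrees of freedom.
- 18/18: noncentrality 0.90 × √9 = 2.70; two-sided power 0.746.
- 20/20: 0.792.
- 20/21: 0.802, so 41 are needed.
- 21/21: 0.812, so 42 with equal arms.
- One-sided, 16/16: 0.800, so 32.

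The normal approximation gives 40 two-sided and 32 one-sided. None of these is 36. With 18 per group, two-sided, 80% power needs d = 0.96 (f = 0.48).

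**5. What does give 36.** Each route below needs an input that the plan leaves out.
- Between-group repeated-measures test, λ = f²Nm/(1 + (m − 1)ρ), with 1 and N − 2 degrees of freedom. N = 36 results for m = 2 measures with ρ from 0.65 to 0.75, m = 3 with ρ from 0.74 to 0.81, or m = 4 with ρ from 0.77 to 0.83. For example, m = 2 and ρ = 0.7 give λ = 0.2025 × 36 × 2/1.7 = 8.58 and power 0.812.
- One baseline covariate, λ = f²N/(1 − r²), with 1 and N − 3 degrees of freedom. N = 36 results for r from about 0.36 to 0.42.

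**The case against.** **Ordinary designs give 36.** This stands. Repeated measures or a covariate at plausible correlations reach it, so the number may have come from a sound calculation. That makes it under-specified, not shown to be wrong.

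**The two-group t-test is not the planned test.** This also stands. The between-group analyses are a kernel test and a mixed model. A reader might infer that the planned comparisons have only 75% power, or that the trial is underpowered. The documents support neither: the 75% belongs to a reference calculation on a single measure.

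**Perhaps 36 is the size of a source study.** The wording allows it, but the sentence on power and alpha speaks of calculations in the plural, 36/0.9 returns the proposed total, and the stimulation pilot described in section 2 had 14 participants. If the reading were right, the f = 0.45 calculation would have no stated result, and the paragraph would still need correcting.

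**The attrition gap is trivial.** Largely true. It is one participant. The requirement also depends on method: a fixed-predictor regression with r² = 0.20 (f² = 0.25) needs 34, and a simulated t-test of r at n = 36 has power of about 0.80. H2b itself will use support vector regression, so r² = 0.20 is only a planning proxy. The 10% refers to the 8-week follow-up, so more than 36 may be available at the earlier assessment, and section 9 plans to keep collecting data after withdrawal. Even so, 37 is the plan's own figure, and its own attrition rate takes 40 below it.

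**It is a pilot.** Section 17's 12 to 20 per group supports 40 unaided, and 18 per group after attrition is still within that range. This limits the consequence, but it does not make the 80% statement verifiable.

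**Conclusion.** Both parts hold, and the issue is minor.

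The attrition shortfall follows from the plan's own numbers: 36 completers against a stated need of 37. By Fisher z, the method that reproduces 37, power is about 79% in place of 80%.

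The f = 0.45 part is a gap in the justification. The sample size of 36 cannot be recovered from f, power and alpha alone. The comparison with 41 to 42, and the 75% at 36 completers, assume equal arms and a two-sided test on one measure. They show that the figure is unsupported as written and say nothing firm about the power of the kernel test or the mixed model.

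**What to change.** Keep N = 40 on the pilot rule and rewrite the power paragraph.

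- For the correlation, add: *With 36 completers after 10% attrition, power for r² = 0.20 is about 79% (Fisher z).*
- For f = 0.45, state the test, sidedness, number of measures and correlation (or covariate) that give 36.
- If those inputs cannot be given, drop the 80% claim for f = 0.45 and write: *As a reference calculation, a simple two-sided two-group comparison at alpha 0.05 with 18 per group has about 75% power for f = 0.45 and 80% power for d of about 0.96. This is not the power of the planned kernel test or mixed model.*

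The cost is one paragraph of wording and possibly a slightly lower stated power. No participants are added and no analysis changes.

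### The stated 0.80 power covers neither the active-versus-sham fMRI tests (H1a, H1b) nor the between-arm NPI test (H2a)

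*Combined protocol and SAP*

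**What the plan says.** Section 17 (Data Analysis Plan) describes a mechanistic pilot that will inform the effect size for a later trial, and cites a rule of 12 to 20 subjects per group. It then adds two formal calculations.

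- First: "The sample size calculation is based on the effect size of LPG related tDCS on visual attention performance", with f = 0.45 and n = 36.
- Second: "the effect size of correlation between NPS-shared neural circuit and patient-report NPI-Q was" r² = 0.70 in previous work. The plan lowers this to r² = 0.20 and obtains n = 37.

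Of both it says: "All of these calculations are based on power at 0.80 and alpha at 0.05". With 10% attrition it arrives at 40 participants.

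Section 4 (Study Design) gives the primary endpoints as "Resting-state and visual attention task-related fMRI" and the secondary endpoints as study partner-rated NPI and NPI-Q scores. Its other measures include cognitive batteries, but not performance on the visual attention task.

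The between-arm tests in Section 17 are a two-sample kernel test on LPG activation (H1a), a two-sample kernel test on change in LPG connectivity (H1b), and a mixed model with a composite test of NPI change (H2a). H2b is a leave-one-out support vector regression of change in NPI on change in activation or connectivity. No effect size or power is given for any of these four analyses as planned.

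**The concern.** A power figure informs only about the quantity and test for which it was computed. The causal question in Section 1 rests on active-versus-sham contrasts, and H1a, H1b and H2a are stated as directional hypotheses to be tested. The sample size paragraph comes directly before those tests, so a reader could carry the 0.80 over to them.

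What is at stake is how a null result is read. If 0.80 power is thought to apply, a non-significant fMRI or NPI comparison may count as evidence against the circuit hypothesis. The plan gives no basis for that reading, and with about 36 completers a moderate difference could easily be missed.

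**Working it through.** **Inputs.** From Section 17: f = 0.45 with n = 36; r² = 0.20 with n = 37; power 0.80; alpha 0.05; attrition 10%; total 40. From Section 4: two arms. Assumed because not stated: two-sided tests and 1:1 allocation. Expected completers: 40 × 0.90 = 36, so 18 per arm.

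**Step 1: the first calculation.** For two equal groups d = 2f = 0.90. An exact two-sided t-test needs 42 in total (41 by ANOVA with N unrestricted, 40 by the normal approximation). A one-sided test needs 32. Exact power at N = 36 is 74.6%. The stated 36 appears only under unstated assumptions, for example a repeated-measures between-group test with two measurements correlated at 0.7. The plan does not name the test behind n = 36, so the figure cannot be verified; it is not shown to be wrong. That is a separate matter from this point.

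**Step 2: the second calculation.** With r = √0.20 = 0.447, Fisher's z gives

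n = [(1.960 + 0.842) / atanh(0.447)]² + 3 = (2.802 / 0.481)² + 3 = 36.9, so 37.

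This reproduces the plan's figure. With the expected 36 completers the power is 78.9%, a trivial shortfall.

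**Step 3: set the calculations beside the planned analyses.**

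| Hypothesis | Planned analysis | Calculation that addresses it |
|---|---|---|
| H1a, LPG activation, active v sham | two-sample kernel test | none |
| H1b, LPG connectivity change, active v sham | two-sample kernel test | none |
| H2a, NPI change, active v sham | mixed model, composite test | none |
| H2b, circuit change predicting NPI change | leave-one-out support vector regression | proxy only (r² = 0.20) |
| Attention performance, active v sham | not planned | f = 0.45 |

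The visual attention task does appear in the primary endpoint, but H1a tests GLM coefficients for LPG activation, not how well participants perform the task.

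**Step 4: a benchmark.** The documents give no effect size for the between-arm fMRI or NPI tests, so their power cannot be computed. For scale, take a two-sample t-test on one change score, two-sided 0.05, n = 18 per arm. The degrees of freedom are 2 × 18 − 2 = 34 and the noncentrality is d√(n/2) = d√9 = 3d. From the noncentral t distribution:

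| Assumed standardised difference | Noncentrality | Power |
|---|---|---|
| 0.3 | 0.90 | 14% |
| 0.5 | 1.50 | 31% |
| 0.8 | 2.40 | 65% |
| 0.96 | 2.88 | 80% |

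If all 40 completed (20 per arm), the difference detectable with 80% power would be 0.91.

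**The case against.** **The trial is a pilot and says so.** Section 17 aims to inform a later trial's effect size, Sections 4 and 16 call it Stage 0, and 20 per group meets the cited rule. The plan names what each calculation refers to and nowhere claims 0.80 power for the kernel tests or the NPI comparison. All of this stands and lowers the severity. It does not remove the point, because the plan goes beyond the pilot rule to formal calculations and then tests directional hypotheses to which they do not apply.

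**The NPI is not wholly without a calculation.** A reader might infer that nothing involving the NPI has been powered. The documents do not support that. The second calculation links the circuit to the NPI-Q, reproduces at 37, and bears on H2b, whose result is summarised by an adjusted R² of observed against predicted NPI. It is an imperfect proxy: a simple correlation, not a cross-validated regression of change on change. Section 17 calls that NPI-Q patient-reported, while Section 1 calls it study partner-rated for the same cited work. This is probably a slip of wording and says nothing about power.

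**The source of f = 0.45 is not given.** It is tempting to trace it to the feasibility study of 14 cognitively normal adults in Section 2 and to criticise it on that ground. The documents do not make that link, so the criticism cannot be sustained.

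**The benchmark is not the planned test.** This also stands. A t-test on a single change score is neither the kernel test nor the mixed model, and 0.96 does not carry over to either. It shows the order of magnitude only.

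**Conclusion.** The point holds in a limited form. The 0.80 power in Section 17 belongs to two quantities: an attention performance effect that the plan never compares between arms, and a simple circuit–NPI-Q correlation that only approximates H2b. The active-versus-sham tests H1a, H1b and H2a have no stated power. On the t-test benchmark, with two-sided 0.05, 1:1 allocation and 36 completers all as described, 80% power needs a standardised difference of about 0.96, and a difference of 0.5 would be detected about 31% of the time.

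A reader might go further and conclude that the trial is shown to be underpowered for its primary endpoints or that 40 is the wrong number. The documents do not support either conclusion: they give no expected fMRI or NPI effect to judge against, and a Stage 0 pilot need not be powered for those contrasts. What needs correcting is the statement of what the 0.80 covers and how null results will be read.

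**What to change.** Revise the sample size paragraph of Section 17 to say three things.

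1. The 0.80 power refers only to the attention performance effect (f = 0.45) and the circuit–NPI-Q correlation (r² = 0.20). No power is claimed for the between-arm fMRI or NPI tests.
2. As a benchmark only (two-sample t-test on one change score, two-sided 0.05, 1:1 allocation assumed, 36 completers), the standardised difference detectable with 80% power is about 0.96, with power of about 31% at 0.5 and 65% at 0.8. Label it as not being the power of the kernel test or the mixed model.
3. Between-arm results will be reported as estimates with 95% confidence intervals, and a non-significant result will not be read as absence of effect.

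Attention performance should not be added as an endpoint to match the calculation. Section 4.2.2 and Table 1 show that a task runs during each session, but not that reaction times are stored for analysis. By the same t-test method, f = 0.45 (d = 0.90) has only about 75% power at 36 completers.

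The cost is a change of wording and a less favourable stated figure. No participants, visits or procedures change.
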